#### Multicenter Studies

In multicenter randomized controlled clinical study, there were some differences affect in different center due to different baseline, clinical practice or other factor, therefore, center effect analysis was required. Analysis will be performed to exclude the center effect.

#### **Examination of Subgroups**

In this study, bridging therapy may be performed within 24h of thrombolysis. Because bridging therapy may be a potential outcome influencing factor, bridging therapy is prespecified as a covariate in the subgroup analysis, and the RR values and 95% confidence intervals of the proportion of the trial and control groups in each subgroup are calculated respectively.

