#### (5) Extend-Ia TNK trial [21-22]

#### Part 1:

The Extend-Ia TNK trial was also aimed at determining whether tenecteplase had a better reperfusion effect than alteplase prior to thrombectomy. The study was a phase II, multicenter, prospective, randomized, open label, blind endpoint, non-inferior-quality study. This study enrolled patients who received thrombolytic therapy for acute cerebral infarction within 4.5h. CTA indicated great artery occlusion (ICA, BA, MCA-M1, and MCA-M2), and thrombectomy could be performed within 6h of onset. They were randomly divided into intravenous tenecteplase 0.25 mg/kg group or alteplase 0.9 mg/kg group according to 1:1.Multimodal CT was performed before thrombolysis, and perfusion was evaluated by angiography (MTICI grade). The primary endpoint was mTICI 22/3 or the proportion of desirable thrombus

disappearance, the secondary endpoint was a 90-day MRS score, 72hNIHSS score decrease of ≥8 points or a ratio of 0-1, and the safety endpoint was SICH and death.

Results: A total of 202 stroke patients were enrolled in this study, 101 subjects received tenecteplase and 101 subjects received alteplase. Primary endpoint Good perfusion rate (Tenecteplase 22% vs. Alteplase 10%) (Ratio difference 12%, 95%CI,2-21, Ratio 2.2, 95%CI, 1.1-4.4; Non-inferiority P = 0.002;P = 0.03).90-day functional outcome of tenecteplase was better than that of alteplase (median mRS 2 vs 3, OR 1.7, 95%CI, 1.0-2.8; P = 0.04). Symptomatic cerebral hemorrhage occurred in 1% of patients in each group.

Conclusion: Tenecteplase has a better rate of vascular recanalization and reperfusion in patients with aortic occlusion.

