#### 4.2 Exclusion criteria

- (1) Patients scheduled to receive endovascular therapy;
- (2) NIHSS score 1A > 2;
- (3) Known to be allergic to rhTNK-tPA and/or rT-PA;
- (4) A history of intracranial hemorrhage;
- (5) A history of severe head trauma or stroke within 3 months;
- (6) A history of intracranial or spinal surgery within 3 months;
- (7) A history of gastrointestinal or urinary tract hemorrhage within 3 weeks;
- (8) A history of major surgery within 2 weeks;
- (9) A history of arterial puncture at sites difficult for compression hemostasis within 1 week.
- (10)Intracranial tumors (except neuroectodermal tumors, such as meningiomas), large intracranial aneurysms;
- (11) Intracranial hemorrhage (including parenchymal hemorrhage, intraventricular hemorrhage, subarachnoid hemorrhage, subdural/extradural hematoma, etc.);
- (12) Active visceral bleeding;
- (13) Aortic arch dissection found.
- (14)Uncontrollable hypertension upon active antihypertensive treatment: systolic blood pressure ≥180 mm Hg, or diastolic blood pressure ≥100 mm Hg;
- (15)Propensity for acute bleeding, including platelet counts of less than 100×10^9/ L or otherwise;
- (16)Blood glucose <2.8 mmol/L or >22.22 mmol/L;
- (17)On oral warfarin anticoagulant treatment with INR>1.7 or PT > 15s;
- (18) Having received heparin treatment within 24 h;
- (19) Having received thrombin inhibitors or factor Xa inhibitors within 48 h;
- (20) Head CT or MRI shows a large infarction (infarcted area > 1/3 of the middle

cerebral artery).

- (21) Subjects who are unable or unwilling to cooperate due to hemiplegia (Todd's palsy) after epileptic seizure or other neurological/psychiatric disorders;
- (22)Pregnant women, lactating women, or subjects who do not agree to use effective contraception during the trial;
- (23) Participation in other clinical trials within 3 months prior to screening;
- (24)Unsuitability for participation or participation in this study as judged by the investigator may result in exposure to greater risk.

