#### 6.2 Concomitant treatment

All enrolled subjects should be treated in the Acute Stroke Unit or, if needed, in the Intensive Care Unit (ICU). All subjects will be enrolled according to the *Chinese Guidelines for the Diagnosis and Treatment of Acute Ischemic Stroke 2018*. [28] Subsequent standardized early treatment management and secondary prophylactic medication are performed. Subjects are treated with thrombolysis according to relevant guidelines (*Chinese Guidelines for Endovascular Treatment of Acute Ischemic Stroke 2018*). [29], *Chinese Guidelines for Early Intravascular Interventional Diagnosis and Treatment of Acute Ischemic Stroke 2018*[30]), and it is up to the investigator to make the final decision on whether or not to perform endovascular treatment, and to record the treatment method and drug combination.

Concomitant drugs (including anticoagulants, defibrillators, antiplatelet agents, lipid-lowering agents, antihypertensive agents, hypoglycemic agents, etc.) before and after randomization and during hospitalization and follow-up should be recorded. Non-therapeutic drugs such as contrast agents, pre-flushing tube heparin, etc., are not recorded as concomitant drugs.

- (1) If the subject does not receive mechanical thrombotomy, no antiplatelet drugs, anticoagulants, defibrillators, thrombolytic drugs or drugs that may affect platelet and clotting function are allowed to be used within 24 hours after the study drugs is used.
- (2) If the subjects have received mechanical thrombotomy but do not receive emergency stent implantation, the investigators will determine whether the concomitant use of antiplatelet and anticoagulant therapy is necessary according to relevant guidelines within 24h after the use of the study drugs, and the concomitant use of drugs will be recorded.
- (3) If the subjects have received emergency stent implantation, antiplatelet agents and anticoagulants can be used within 24 hours after the study drugs is used.
- (4) Any medication other than those listed above (including blood pressure lowering, blood glucose lowering, lipid-lowering drugs, etc.) is allowed. If necessary,

the investigator should carefully consider administering a relatively stable and safe dose to the subject.

During the study period, any treatment and/or prescriptions issued prior to randomization or any medication changes during the study period should be recorded on an electronic case report form.

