#### Include:

- 1) The proportion of subjects with an mRS score of 0-2 at  $90\pm7$  days
- 2) MRS level distribution at 90±7 days (Shift Analysis /Ordinal Distribution)
- 3) The proportion of subjects whose NIHSS score is 0-1 or is improved compared to the baseline with  $\Delta$  NIHSS  $\geq$  4 at 24±2h, 7±1d or before discharge (whichever comes first)
- 4) Health-related quality of life (EQ-5d) at 90±7 day
- 5) The proportion of subjects with a Bathel score  $\geq$  95 points at 90±7 days

The analysis of secondary endpoints refers to the general principles of statistical analysis. For secondary efficacy outcomes, common odds ratio with its 95% confidence interval was calculated using ordinal logistic regression for the outcome of ordinal 90-day mRS score, and odds ratios with their 95% confidence intervals were calculated using binary logistic regression for other secondary efficacy outcomes.

Subgroup analysis: In this study, bridging therapy is performed within 24h of thrombolysis. Because bridging therapy may be a potential outcome influencing factor, bridging therapy is predesigned as a covariate in the subgroup analysis, and the RR values and 95% confidence intervals of the incidence of the trial and control groups in each subgroup are calculated respectively.

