#### Interactions with Subgroups

In this study, bridging therapy is prespecified as a covariate in the subgroup analysis. The RR values and 95% confidence intervals of the incidence of the trial and control groups in each subgroup are calculated respectively. Summary tables will be produced for the predefined subgroups and interactions between treatment and these subgroups will be investigated, using a logistic regression model. A separate model will be used for each interaction to determine its significance.

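### The only named subgroup factor, bridging therapy, is decided after randomization by an unmasked investigator, so its RRs and interaction test are liable to bias of unknown size and direction

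*Supplement*

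**What the plan says.** SAP section 9 (Examination of Subgroups) states that "In this study, bridging therapy may be performed within 24h of thrombolysis" and continues: "Because bridging therapy may be a potential outcome influencing factor, bridging therapy is prespecified as a covariate in the subgroup analysis". RRs with 95% CIs are to be given for each subgroup. SAP section 12 (Interactions with Subgroups) repeats that "bridging therapy is prespecified as a covariate in the subgroup analysis" and adds that "interactions between treatment and these subgroups will be investigated, using a logistic regression model", with a separate model for each interaction. That section speaks of subgroups in the plural but names no other factor.

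Protocol V2.2 agrees. Section 12.4 says "In this study, bridging therapy is performed within 24h of thrombolysis" and plans the same subgroup RRs, and the protocol summary also splits the primary endpoint by bridging. Neither document names a baseline subgroup, and neither adds a caution about a split made after randomization.

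Three other protocol passages bear on the point. Section 4.2, criterion (1), excludes "Patients scheduled to receive endovascular therapy". Section 6.2 says "it is up to the investigator to make the final decision on whether or not to perform endovascular treatment". Appendix 1, marked as for reference only, allows endovascular treatment to be considered when intravenous thrombolysis has failed.

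**The concern.** A subgroup RR compares like with like only if membership is fixed before treatment or cannot be changed by it. Here membership is settled after the study drug has been given, by someone who knows which drug it was, and possibly in the light of how the patient responded. If one drug opens more vessels early, fewer of its patients go on to bridging, and those who do are a different mix from the bridged patients in the other arm. Investigators could also choose differently by arm.

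The risk is one of interpretation. An equally good drug could look worse among bridged patients, or better, and the interaction p-value would be read as showing whether benefit depends on bridging, which it cannot show. This is also the trial's only prespecified analysis of effect modification, so any baseline subgroup reported later would be post hoc.

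**Working it through.** **1. Timing and decision.** Protocol 4.2 removes patients whose endovascular treatment is already scheduled. Both documents place bridging within 24 h of thrombolysis, and thrombolysis follows randomization (Protocol 6.1). The trial is open label (3.1) and the randomization system tells the site the arm (3.4.1). Blinding in 3.4.2 covers endpoint assessment, not the investigator who decides on endovascular treatment under 6.2. The factor is therefore set after randomization by an unmasked person.

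**2. Possible dependence on the drug.** Appendix 1 links endovascular treatment to failed thrombolysis. The background (Protocol 1.3 (5), Part 1) cites "Good perfusion rate (Tenecteplase 22% vs. Alteplase 10"%), that is, reperfusion of 22% with tenecteplase and 10% with alteplase before thrombectomy. Together these make an effect of the drug on who is bridged plausible.

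**3. The plan's own figures.** No bridging rate or subgroup size is given, so there is none to reproduce. The stated 642 per group does reproduce: control 0.5932, treatment 0.5932 × 1.07 = 0.6347, margin 0.937, one-sided alpha 0.025 and power 0.85 give 642 by the Farrington-Manning score method (643 by Wald on log RR). It contains no bridging term and does not depend on the subgroup plan.

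**4. Illustration.** Suppose the drug has no effect on 90-day mRS 0-1 in any type of patient, so the true RR is 1 in each type. Inputs:

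- From the protocol: early reperfusion 22% vs 10%, taken here to remove the need for bridging.
- Assumed, not in the documents: share with large-vessel occlusion 10% to 30%; mRS 0-1 rate 65% without occlusion, 30% if reperfused early on neither drug, 60% if on either drug, and m = 35% to 55% if on tenecteplase only.

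Per 100 occlusion patients, 78 are bridged on tenecteplase and 90 on alteplase. The extra 12 are those who would reperfuse early on tenecteplase only.

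- Bridged rate, tenecteplase: 30%.
- Bridged rate, alteplase: (78 × 0.30 + 12 × m) / 90.
- The occlusion share cancels from the bridged RR.

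At a 20% occlusion share, 15.6% of tenecteplase and 18.0% of alteplase patients are bridged:

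| m | Bridged rate, alteplase | RR, bridged | RR, not bridged | Ratio of RRs |
|---|---|---|---|---|
| 35% | 30.7% | 0.978 | 0.987 | 0.991 |
| 45% | 32.0% | 0.938 | 0.991 | 0.946 |
| 55% | 33.3% | 0.900 | 0.996 | 0.904 |

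At m = 45% the non-bridged rates are (0.80 × 0.65 + 0.02 × 0.60) / 0.82 = 64.9% on alteplase and (0.80 × 0.65 + 0.02 × 0.60 + 0.024 × 0.45) / 0.844 = 64.3% on tenecteplase, an RR of 0.991. The overall rate is 59.0% in both arms, RR 1. Over shares of 10% to 30%, the non-bridged RR runs from 0.978 to 0.998 and the ratio of RRs from 0.90 to 1.00. If early reperfusion is set to 10% in both arms, so that the drug does not affect bridging, both subgroup RRs return to 1.00. The distortion comes from the conditioning alone.

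**5. Size against noise.** With 715 per arm, 15.6% and 18.0% are about 112 and 129 patients. For rates of 30% and 32%, SE(log RR) = √(0.70/(0.30 × 112) + 0.68/(0.32 × 129)) = 0.193. A 95% CI around 0.938 then runs from about 0.64 to 1.37.

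**The case against.** The reperfusion figures come from patients with large-artery occlusion who were about to undergo thrombectomy. This trial excludes such patients if the procedure is already scheduled, so what remains is unplanned bridging, whose frequency and triggers are unknown. The illustrated distortion is small beside the sampling error of a subgroup of that size. No decision rule rests on the subgroup result. Clinicians will also want to know how bridged patients fared.

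Most of this stands, and it limits the claim. The cited figures support plausibility, not a magnitude for this trial. Bias is absent if the drug does not change who is bridged and investigators do not choose differently by arm. But the plan neither states nor examines those two conditions. A wide interval does not make the comparison a randomized one, and clinical interest is met by a descriptive table.

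Three stronger readings are tempting and are not supported:

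- *That the subgroup RRs will be biased against tenecteplase.* The documents fix neither size nor direction, and selection by unmasked investigators could work either way.
- *That an illustrated RR below 0.937 signals failed non-inferiority.* In SAP section 4 that margin applies to the lower 95% limit of the primary RR. No subgroup non-inferiority test is planned.
- *That bridging contaminates the primary result.* The SAP's primary models adjust for center, and for center with baseline mRS. The word covariate is tied to the subgroup analysis. Protocol 12.4 leaves room to adjust for covariates that differ between groups, but does not name bridging there.

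**Conclusion.** The point holds as a liability to bias in a secondary analysis. That bridging is the only named subgroup factor, that it is determined after randomization, and that an unmasked investigator decides on it all follow directly from the final SAP and Protocol V2.2. That it may depend on response to the drug is plausible from Appendix 1 and the cited reperfusion figures, but is not demonstrated for this population. With no drug effect in any type of patient, and on the assumed occlusion shares and outcome rates above, the expected RR is 0.90 to 0.98 in bridged and 0.98 to 1.00 in non-bridged patients, with an overall RR of 1. These numbers show the mechanism and do not predict this trial's result. The primary analysis and the sample size are untouched. The plan should be changed because the correction is easy and the analysis as written invites a causal reading that it cannot bear.

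**What to change.** In SAP sections 9 and 12, Protocol 12.4 and the protocol summary:

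- Remove bridging as a subgroup factor and covariate, and drop the treatment-by-bridging interaction test.
- Report endovascular use by arm as a post-randomization outcome. If outcomes are tabulated by bridging status, label the table descriptive only.
- Apply the planned subgroup RRs and interaction tests to baseline factors already collected, such as baseline NIHSS, age and onset-to-randomization time, with cut-points fixed in advance. Onset-to-treatment time should not be used: drug is given after randomization, and in an open-label trial with different preparations the delay can differ by arm.

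The cost is wording only. Protocol 7.1 collects age, NIHSS and onset time at screening, and the flow chart notes already ask for bridging information. The team should confirm that the time of randomization can be exported from the central system. A baseline vessel-occlusion subgroup may not be possible, since screening imaging is only CT or MRI. The downside is that a split of clinical interest becomes descriptive. Who receives bridging does not change.

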#### Multiple Comparisons and Multiplicity

A single primary efficacy variable has been defined for this study, with all other efficacy variables were identified as secondary or other. Similarly, only one treatment comparison is of interest in the study and therefore there are no requirements to adjust for multiple comparisons or multiple endpoints within this study.

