#### Secondary Efficacy Endpoints:

- 6) The proportion of patients with an mRS score of 0-2 at 90±7 days;
- 7) MRS level distribution at 90±7 days (Shift Analysis /Ordinal Distribution);
- 8) The proportion of patients whose NIHSS score is 0-1 or is improved compared to the baseline with  $\Delta$ NIHSS  $\geq$  4 at 24±2h, 7±1d or before discharge (whichever comes first);
- 9) Health-related quality of life (EQ-5D) at 90±7 day;
- 10) the proportion of patients with a Bathel score ≥ 95 points at 90±7 days;

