#### 4. Statistical Hypotheses

Comparison of the primary efficacy endpoint between groups is conducted by a one-sided test, with a significance level of one-sided  $\alpha$ =0.025. Null hypothesis H0: RR  $\leq \Delta$  and alternative hypothesis H1: RR  $> \Delta$ ; when P < 0.025, or lower limit of 95% CI of RR  $> \Delta$ , it indicates that the test drug is not inferior to control drug; RR is the ratio of incidence of the treatment group and the control group,  $\Delta$  is the non-inferior margin, 0.937 in this trial. All other statistical analyses are conducted by two-sided tests, with a significance level of two-sided  $\alpha$  =0.05. When P  $\leq$  0.05, it indicates a statistically significant difference. Non-inferiority hypothesis tests are as follows:

H0: 
$$RR$$
 Treatment group/control group  $\leq \Delta$   
H1:  $RR$  Treatment group/control group  $> \Delta$ 

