#### 12. Efficacy Analyses

Primary efficacy analysis will be performed using FAS and PPS populations. The analyses for the primary efficacy endpoint will be conducted by one-sided test with a significance level of one-sided  $\alpha$ =0.025. All other statistical analyses will use a 2-sided test at the 5% level of significance.

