#### **Adverse Events**

Adverse events (AEs) will be coded using the MedDRA coding dictionary (Version 6.0 or a later release) and grouped by system organ class (as detailed in the study protocol). Separate data display listings and summaries will be presented for adverse events that start prior to first dose of study medication (pre-treatment), whilst on study medication (during treatment) and after the last dose of study medication (post-treatment).

Within each treatment group, the number and percentage of patients experiencing an AE will be summarized by system organ class and preferred term and Chi-squared test or Fisher's Exact test will be used to compare the number of each grouped AE event between treatment groups. In addition, a separate summary will be provided for AEs experienced by more than 5% of patients in either of the treatment groups.

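### Five secondary efficacy endpoints are each declared significant at P≤0.05 with no hierarchy, no gate on the primary result and no supportive label, so the family-wise chance of a false secondary finding is uncontrolled

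*Supplement*

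**What the plan says.** SAP section 9 (Multiple Comparisons and Multiplicity) gives the premise, "A single primary efficacy variable has been defined for this study, with all other efficacy variables were identified as secondary or other", adds that only one treatment comparison is of interest, and concludes "therefore there are no requirements to adjust for multiple comparisons or multiple endpoints within this study".

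The primary endpoint, mRS 0-1 at day 90, is tested one-sided at 0.025 for non-inferiority against an RR margin of 0.937. Superiority (RR above 1) is tested only if non-inferiority is met (protocol 12.2; SAP section 12, Main Model).

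For everything else, SAP section 12 states: "All other statistical analyses will use a 2-sided test at the 5% level of significance". SAP section 4 and protocol 12.2 add the decision rule: when P≤0.05, "it indicates a statistically significant difference".

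SAP section 3 lists five secondary efficacy endpoints: mRS 0-2, the ordinal mRS distribution, NIHSS response, EQ-5D and Barthel ≥95. The Secondary Efficacy Analyses part of section 12 gives each one a between-group test and an odds ratio or score difference with a 95% CI. Neither current document gives these endpoints a testing order, an alpha split, a condition on the primary result, or a label such as supportive, exploratory or nominal.

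**The concern.** A single primary variable protects the claim made on that variable. It does not protect the other endpoints, which the SAP exempts on the same ground. Leaving secondaries unadjusted is an accepted choice when they are declared supportive. Here the waiver is combined with an explicit rule for declaring significance, and the plan says nothing about how such a declaration should be read. As written, a secondary endpoint at P=0.04 is a statistically significant difference even if primary superiority, or non-inferiority itself, has failed.

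This matters because the protocol intends to look for superiority (Introduction and 12.2), but the trial is sized for non-inferiority. If the primary superiority test is neutral, an isolated secondary P value would be the most visible sign of a difference, and the plan does not limit the weight it may carry.

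**Working it through.** **1. The plan's own figure.** The documents state no family-wise error rate for the secondaries. The nearest figure to check is the sample size, which shows whether the primary level is used consistently. Inputs (SAP section 6): control rate 0.5932, RR 1.07, margin 0.937, one-sided 0.025, power 0.85. The treatment rate is 1.07 × 0.5932 = 0.6347.

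n per group = [(1−pT)/pT + (1−pC)/pC] × [(z0.975 + z0.85)/(ln RR − ln margin)]²
= (0.5755 + 0.6858) × [(1.960 + 1.036)/(0.0677 + 0.0651)]² = 642.8.

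A Farrington-Manning score calculation gives 642.0. The stated 642 per group is reproduced. With 10% dropout, 642/0.9 and 643/0.9 round up to 714 and 715, in line with the stated 715. The primary level is consistent.

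**2. Is a neutral superiority result plausible?** Use the sponsor's rates (63.64% and 59.32%) with 642 per group. ln RR = 0.0703. SE = √[(0.3636/0.6364 + 0.4068/0.5932)/642] = 0.0443, so the expected z is 1.59. Power for superiority at one-sided 0.025 is Φ(1.59 − 1.96), or about 36%. Even under the planning assumptions, superiority is more likely to be missed than shown.

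**3. Family-wise rate for the five secondaries.** Inputs: k = 5 endpoints (SAP section 3), two-sided 0.05 each (SAP section 12), all five nulls true.

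Independent tests: 1 − 0.95⁵ = 22.6%.

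The endpoints are not independent. Four are day-90 function or quality-of-life measures, and two of those come from the same mRS score. With equicorrelated normal test statistics and rejection at |z| > 1.96 (simulation, 2 million draws):

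| Assumed common correlation | At least one false significance |
|---|---|
| 0 | 22.6% |
| 0.3 | 20.9% |
| 0.5 | 18.3% |
| 0.7 | 14.9% |
| 0.9 | 10.2% |

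A pattern closer to the likely structure sets the four day-90 measures at 0.8 with each other and NIHSS response at 0.4 with the rest. It gives 15.1%. These correlations are also assumed.

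**4. Sensitivity to counting.**
- Counting only false findings in favour of tenecteplase, independence gives 1 − 0.975⁵ = 11.9%.
- The NIHSS endpoint names both 24 hours and 7 days or discharge. Counted as two tests, independence gives 1 − 0.95⁶ = 26.5%.
- The four mRS, NIHSS and Barthel endpoints are each tested twice (chi-squared or Wilcoxon, plus logistic). The two tests nearly coincide, so this adds little.

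**The case against.** The best defence is that the confirmatory claim rests on one gated sequence, so the secondaries need no adjustment. Protocol 12.2 reserves the conclusion that the test drug is superior for the primary test. The SAP ranks all other efficacy variables below the primary and already plans estimates with 95% CIs for them. All of this stands, and it confines the point to how secondary P values are interpreted. It does not remove the point, because the same sections still declare significance at P≤0.05 without saying that such a result is only supportive.

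Four stronger readings are tempting, and the documents do not support them:

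- *That the stated 5% is false.* It is a per-test level and it holds per test. The plan never promises a family-wise rate.
- *That the error rate is one definite number, such as 18%.* That value needs an assumed correlation of about 0.5, and the documents give none. Only a range can be defended.
- *That the sponsor plans to claim tenecteplase is better than alteplase on a secondary endpoint.* No text says so. The plan merely does not rule it out.
- *That the same calculation condemns the safety and adverse-event tests.* Family-wise control is the wrong yardstick for screening harms, where a missed signal is the main worry. Several of the safety outcomes are nested (symptomatic haemorrhage within 36 hours, within 90 days, any intracranial haemorrhage), and protocol 12.5 makes adverse-event comparisons only when necessary.

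**Conclusion.** The point holds as a gap in the interpretation rule for secondary efficacy results. If all five nulls are true, the chance of at least one declared significant difference is 22.6% under independence and about 10% to 21% for common correlations of 0.9 to 0.3. That is roughly two to more than four times the per-test level. The range rests on counting NIHSS response as one test and on assumed correlations. Type I error for the primary endpoint is unaffected, and so are the sample size, the estimates and the intervals. It is a worthwhile and inexpensive correction that does not threaten the primary conclusion.

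**What to change.** Replace the closing statement of SAP section 9 (Multiple Comparisons and Multiplicity) with text to this effect:

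*The only confirmatory tests are non-inferiority (RR margin 0.937) and, if met, superiority (RR above 1) of mRS 0-1 at day 90, in that order, each at one-sided 0.025. Secondary efficacy and subgroup results are supportive. They are reported as effect estimates with unadjusted 95% confidence intervals; their P values are nominal and no claim of a statistically significant difference rests on them.*

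Narrow the P≤0.05 sentence in SAP section 4 and protocol 12.2 to match. If the sponsor wants a confirmatory secondary claim, append the chosen endpoint or endpoints to the fixed sequence after superiority, each at two-sided 0.05, stopping at the first failure. This keeps the family-wise level without splitting alpha.

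The cost is wording only, with no added patients or data. The real price is that an isolated secondary P≤0.05 can no longer be called a demonstrated difference.
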